#### **10.3.4.2 Analyses of Secondary Efficacy Endpoints**

Similar models to those described above will be applied to analyzing changes in other PFT parameters, HRCT fibrosis score, and patient-reported outcome.

#### **10.3.4.3 Analysis of Progression Free Survival**

PFS is defined as the time from randomization to the first occurrence of the following events during the study (whichever occurs first):

1. Death from any cause
2. Absolute decline FVC percent of predicted value of  $\geq 10\%$  not due to intercurrent illness confirmed by repeat spirometry
3. Clinical diagnosis of progression of IPF

The analysis of PFS will be based on the Safety Population. If no PFS event is observed during the study, then PFS is censored at the last PFT assessment.

Comparison between treatment arms in PFS will be performed using the Cox regression model with adjustment for baseline FVC % predicted value as well as stratification and stratification by treatment interaction.

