##### 4.2.3.1 Subjects Enrolled under the Original Protocol and Assigned to Arm A: FG-3019

All subjects in Arm A whose FVC percent predicted value shows less than 3% absolute decrease from baseline in the Randomized Treatment Period will be offered participation in an Extended Treatment Period. These subjects may continue treatment until FVC percent predicted decreases 3% or more on two consecutive scheduled evaluations compared to the original pre-treatment baseline.

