### **4.2.4 End of Treatment and Follow-up**

#### **4.2.4.1 Randomized Treatment Phase**

- Subjects assigned to either FG-3019 or placebo who discontinue treatment before week 48 should undergo end of treatment and safety assessment visits (Appendix 3).
- Subjects who were assigned to FG-3019 complete 48 weeks of treatment and are not going on to the Extended Treatment Period should undergo a Safety Assessment visit (Appendix 3); Week 48 evaluation is identical to End of Treatment visit. Thus, subjects who complete Week 48 and are not eligible for the extension study only need the final safety assessment. Subjects who enter the Extended Treatment Period do not need a final safety assessment because they are continuing treatment).
- Subjects who were assigned to placebo who complete 48 weeks of treatment but do not enter the Extended Treatment Period should undergo a safety assessment as described in Appendix 3.

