## **10.3 Statistical Analysis**

### **10.3.1 General Analysis Methods**

Unless the planned interim analysis at the end of the Randomized Treatment Phase indicates a lack of efficacy, the study is completed when the last subject completes the last visit in the Extended Treatment Phase.

Baseline characteristics, safety, and biomarker data will be summarized based on available data in the Safety Population, except for the parameters indicated otherwise. The primary efficacy analyses will be based on the FAS population, except for the analysis of PFS, which will be based on the Safety Population. All safety, efficacy, and exploratory endpoints will be summarized by group of actual treatment received.

All randomized subjects will be included in the data listings.

Continuous variables will be presented by descriptive statistics: n, mean, standard deviation, or standard error, median, minimum, and maximum. Categorical variables will be presented by counts of subjects and percentage.

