### Appendix 3. Schedule of Assessments – Early Termination/End of Treatment and Follow-up Visit

Assessment	Early Termination/End of Treatment a	End of Study
1. SGRQ	X b	
2. Vital Signs	X b	X
3. Complete Physical Exam	X b	
4. Spirometry	X b,c	
5. CBC with Differential	X b	
6. Serum Chemistry	X b	
7. Spot Urine for Urinalysis	X b	
8. Pregnancy Test d	X b	X
9. HRCT of Chest	X b	
10. 12-Lead ECG	X b	
11. Serum and Plasma Biomarkers	X b	
12. Plasma HAHA		X
13. AEs and SAEs e	X b,e	X b,e
14. Concomitant Medications f	X b	X
15. Procedures and Nondrug Therapies	X b	X
16. Subject Disposition	X	X

Abbreviations: AE = adverse event; CBC = complete blood count; ECG = electrocardiogram; HAHA = human anti-human antibody; HCG = human chorionic gonadotropin; HRCT = high resolution computed tomography; PFT = pulmonary function test; SAE = serious adverse event; SGRQ = Saint George's Respiratory Questionnaire.

- a End of treatment, including due to withdrawal/progression evaluation preferably 3 weeks after last dose of study drug for all subjects who have received more than 4 doses of FG-3019. The End of Study, final safety assessment should be 4 weeks after last dose of study drug. Study windows are  $\pm$  3 days
- b Subjects who completed the withdrawal/progression evaluations at Week 48 or for early withdrawal do not need to repeat them. Study endpoint evaluations do not require repetition if performed within 8 weeks, HRCT does not require repetition if performed within 4 months, and safety assessments, such as clinical laboratory tests, do not require repetition if performed within 2 weeks.
- c Spirometry .
- d Pregnancy tests for women of childbearing potential only: urine pregnancy tests at all Extended Treatment Period visits. A positive urine pregnancy test must be confirmed by serum HCG.
- e See Sections 4.7 and 11.3.1 for follow-up of AEs.
- f Refer to Section 4.6.1 for prohibited concomitant medications.

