2.2 Assessments in Extended Treatment Period

- FVC and FEV1 are assessed at 12-week intervals.
- HRCT scan of the chest is performed at 24-week interval during extension period.
- SGRQ questionnaire is administered at 12-week intervals.
- Electrocardiogram (ECG) is assessed at 24-week intervals.
- Laboratory samples for safety assessments are collected at 6-week intervals.
- Serum and plasma samples for biomarker tests (including CTGF) are collected at 24-week intervals.
- Plasma samples for assessing HAHA are collected prior to dosing on Day 1 of Extension Period and at the End of Study (EOS) safety follow-up.
- Adverse events, concomitant medications, procedures, non-drug therapies, oxygen use are collected from signing ICF through End of Study (EOS).

- Vital signs are measured at every clinical visit. On dosing days, vital signs are measured at pre-, intra-, and post-infusion.
- Physical examination is performed at 6-week intervals.

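### The between-arm PFS analysis has no Week 48 limit and no timing for the confirming spirometry, so follow-up that differs by arm can enter it

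*Protocol*

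**What the plan says.** - **Protocol 10.3.4.3.** "PFS is defined as the time from randomization to the first occurrence of the following events during the study". The events are death, an absolute fall of at least 10 points in FVC % predicted "not due to intercurrent illness confirmed by repeat spirometry", and clinical diagnosis of progression. "If no PFS event is observed during the study, then PFS is censored at the last PFT assessment". The arms are compared by a Cox model adjusted for baseline FVC, stratification and its interaction with treatment.
- **Protocol 10.3.1.** Unless the analysis at the end of the randomised phase shows lack of efficacy, "the study is completed when the last subject completes the last visit in the Extended Treatment Phase".
- **Protocol 4.2.3.1 to 4.2.3.3.** Original-protocol Arm A (FG-3019) subjects may extend only if they are among those "whose FVC percent predicted value shows less than 3% absolute decrease from baseline in the Randomized Treatment Period". From Amendment 1 on, FVC must exceed the original baseline, and treatment ends after two successive values at or below it. Every placebo subject is offered FG-3019, with Week 48 as a new baseline for FVC change.
- **Protocol 4.2.4.1 and Appendix 3.** "Thus, subjects who complete Week 48 and are not eligible for the extension study only need the final safety assessment". That visit has no spirometry, and a footnote adds: "Study endpoint evaluations do not require repetition if performed within 8 weeks".
- **SAP (Part 2) 2.2.** In the extension, "FVC and FEV1 are assessed at 12-week intervals". Protocol Appendix 2 puts the first at Week 12-EX.
- **Protocol 3.2.2.** Respiratory death is censored at Week 52. Progression has no limit, and its clock starts at Day 1, not at randomisation.

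**The concern.** There are two separate problems.

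**The window.** The lock in 4.2.2 waits for the last subject's Week 48, so earlier enrolees may already have extension data. A Cox model that follows 10.3.4.3 literally would then compare a small Arm A group selected on good FVC with nearly all of placebo, now on active drug. Arm A's extension treatment also ends well short of a 10-point fall. Section 10.3.4.3 does not name the baseline for a placebo decline after Week 48.

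**The confirmation.** A first 10-point fall at Week 48 makes an Arm A subject ineligible for the extension, and no further spirometry is scheduled. A placebo subject with the same fall can extend and be tested 12 weeks later. If the repeat means the next scheduled test, the same decline can be confirmed on schedule in one arm only. A Week 48 cut on event onset does not cure this.

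At stake is a secondary endpoint whose hazard ratio could favour FG-3019 when the drug does nothing.

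**Working it through.** **1. The plan's own figure.** The only sizing statement (Protocol 10.1) is about 80% power for Week 48 FVC % predicted. Inputs: 55 per arm, 10% dropout, SD 7.3, difference 7.0 − 2.8 = 4.2, two-sided 0.05.

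- Evaluable per arm: 55 × 0.9 = 49.5.
- 4.2 / (7.3 × √(2/49.5)) = 2.86; power = Φ(2.86 − 1.96) = 81.7% (80.9% by noncentral t).

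This reproduces. No PFS event count, hazard ratio or power is stated.

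**2. Who has extension follow-up under the null.** Take a Week 48 change with mean −7.0 and SD 7.3 in both arms.

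- Arm A above baseline: Φ(−7.0/7.3) = Φ(−0.96) = 17%.
- Arm A down less than 3 points (original protocol): 1 − Φ(4.0/7.3) = 1 − Φ(0.55) = 29%.
- Placebo: all are offered entry.

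**3. Null simulation: inputs.**

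- From the documents: 68 per arm (136/2), mean −7.0, SD 7.3, 10% dropout, 12-weekly tests, visits within ±3 days, Day 1-EX 0–3 weeks after Week 48.
- Assumed: linear decline with visit error SD 3, scaled to the SD of 7.3 (with error at both visits, slope SD = √(7.3² − 2×3²) = 5.94); deaths 8% per year; clinical progression 0, 10 or 20% per year; all placebo subjects extend; the Amendment 1 entry rule for all of Arm A; original baseline throughout.
- Follow-up stops at the lock. There were 3,000 trials per scenario.

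*Anchored accrual.* Protocol 1.5 reports 27 subjects with multiple blinded doses in a brochure dated 18 December 2014, so their Week 48 fell by about 19 November 2015. If someone was still in the randomised phase at Amendment 5.0 (12 December 2016; assumed), those 27 had at least 389 days = 55.6 weeks before the lock. They get 55.6 weeks; the other 136 − 27 = 109 get uniform 0–55.6.

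**4. Results.** Ranges run over the three clinical-progression rates. False wins are null trials significant for FG-3019 (nominal 2.5%).

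| Rule | Extension follow-up | Hazard ratio | False wins |
|---|---|---|---|
| Week 48 cut, same repeat rule in both arms | none | 1.00–1.01 | 2.2–2.6% |
| As written, repeat at same visit | 0–24 weeks | 1.03–1.05 | – |
| | 0–48 weeks | 0.98–1.00 | 2.4–3.0% |
| | anchored | 0.94–0.98 | 3.1–4.4% |
| | 0–104 weeks | 0.89–0.96 | 3.3–5.4% |
| As written, repeat = next scheduled test | 0–48 weeks | 0.73–0.85 | 8.3–14.7% |
| | anchored | 0.69–0.82 | 11.3–20.8% |
| Week 48 cut, later confirmation left open | anchored | 0.73–0.85 | 7.8–15.5% |
| Same, half of Arm A's Week 48 declines repeated off schedule | anchored | 0.85–0.93 | 3.9–7.0% |
| As written, same-visit repeat, placebo re-baselined at Week 48 | anchored | 1.06–1.10 | – |

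With visits on exact days, the four same-visit ratios as written are 0.95–0.97, 0.88–0.93, 0.84–0.91 and 0.79–0.89. In the anchored same-visit case at 10%, post-Week-48 events average 0.9 in Arm A and 13.1 in placebo. About 6–8 subjects per arm first show the decline at Week 48.

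**5. Sensitivity** (anchored, 10% per year; same-visit as written, then Week 48 cut with open confirmation).

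- Base: 0.96; 0.80.
- Placebo uptake 60%: 0.94; 0.87.
- Visit SD 2 or 4: 0.96–0.97; 0.79–0.81.
- Deaths 4 or 12%: 0.95–0.97; 0.77–0.82.
- Cox adjusted for baseline FVC and stratum, no interaction term, 600 trials: 0.98; 0.81 (fixed cut 1.02).
- Arm A selection removed, as written: 1.01 with same-visit repeat, 1.00 with next scheduled test. Selection therefore drives the bias.

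A harsher case follows everyone eligible who extends to Week 48-EX, with no deaths or clinical progression, placebo uptake of 60–100% and confirmation otherwise at the next scheduled test. It gives 0.68–0.80 if every Week 48 decline is repeated promptly and 0.47–0.62 if none is.

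**The case against.** The strongest reply is that the rule belongs in a document we do not have. The SAP introduction assigns the randomised period to Part 1, and Protocol 7.2 refers to a separate lung function manual. Either may fix the cut and the repeat.

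The supplied text also leans towards Week 48. Section 4.2.2 places the final efficacy assessment there and locks afterwards. Section 10.3.6 times the unblinded analysis to it. Section 3.2.2 carries HRCT and quality of life to later time points but not progression. SAP 3.1 lists no PFS endpoint for the extension, and SAP 4 rules out formal inference. All of that stands as evidence of intent, but none of it sets a per-subject PFS cut. Where the protocol wants a limit, as for respiratory death, it states one.

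On size, several points stand:

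- With a same-visit repeat the effect is small and its sign varies. At 0–48 weeks the false-win rates are within about two Monte Carlo standard errors (0.29 points) of 2.5%.
- The large ratios need the next-scheduled-test reading. Protocol 7.5 allows unscheduled visits and 4.4.3 keeps investigators blinded, so prompt repeats need not differ by arm. Section 8 asks for two consecutive tests, but for removal from treatment and with no interval.
- The anchored accrual rests partly on assumption.
- Stopping at the lock is narrower than the literal end of study. A full 48 weeks of extension for everyone would need PFS rerun after the lock: 0.86–0.93 with ±3-day visits, 0.76–0.86 on exact days, same-visit repeat.

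**Conclusion.** The point holds, with moderate confidence. As written, 10.3.4.3 lets the between-arm Cox comparison take in post-Week-48 data gathered under different entry rules and treatment in the two arms. It also leaves open a confirmation rule that the visit schedule can satisfy in placebo but not in Arm A. A Week 48 comparison was probably intended.

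The window alone matters little for short accrual and modestly for long accrual. Open confirmation matters more if the repeat is the next scheduled test, and a Week 48 cut alone leaves that part in place. The sizes depend on accrual, visit timing, event rates and the readings of confirmation and baseline, none of which the documents fix; they show direction and possible scale, not a forecast. SAP Part 1 could settle both points. Only a secondary endpoint is affected, but it should be fixed before the analysis.

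**What to change.** In Protocol 10.3.4.3:

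1. Limit the between-arm comparison to events with onset on or before the Week 48 visit and before Day 1-EX, and censor event-free subjects at their last test up to that point.
2. Measure FVC decline from the original baseline in both arms.
3. State one rule for both arms for a decline first seen at Week 48. Either (a) date it to Week 48 if confirmed by a repeat obtained on the same schedule in both arms before Day 1-EX, or (b) count it only if confirmed by the Week 48 visit.
4. Use one time origin here and in 3.2.2.
5. Report extension progression descriptively only.
6. Confirm that SAP Part 1 carries the same cut and confirmation rule.

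The cost is two or three sentences and that check. Option (a) needs a repeat spirometry in roughly 4–8 subjects per arm. Option (b) needs none but loses about five events per arm under the null: 20.8 − 15.5 = 5.3 without clinical progression, 24.9 − 20.1 = 4.8 at 10% per year.

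Extension events no longer contribute: 12 of 54 at planning values, anchored accrual and 10% per year. At planning values, PFS power for clinical progression of 0, 10 and 20% per year is 41, 30 and 21% with the cut, against an apparent 56, 40 and 28% as written. That gain comes from Arm A selection: with 0–48 weeks of extension, 10% per year and no selection, power is 30%, the same as with the cut.

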12. DLCO  $< 30\%$  of the predicted value.
13. High likelihood of lung transplantation (in the opinion of the Investigator) within 6 months after Day 1.
14. Poorly controlled chronic heart failure; clinical diagnosis of cor pulmonale requiring specific treatment; or severe pulmonary hypertension requiring specific treatment that, in the opinion of the Investigator, would preclude the subject's participation in the study.
15. Use of medications to treat IPF within 5 half-lives of Day 1 dosing. If monoclonal antibodies were used, the last dose of the antibody must be at least 4 weeks before Day 1 dosing.
16. Use of any investigational drugs, including any investigational drugs for IPF, within 4 weeks prior to Day 1 dosing.
17. History of cancer diagnosis of any type in the 3 years preceding Screening, excluding non-melanomatous skin cancer, localized bladder cancer, or in situ cancers.
18. Clinically significant trauma or surgical procedures within 4 weeks prior to dosing.
19. Planned elective surgery during the study including 4 weeks following the final dose of Study Drug.
20. History of allergic or anaphylactic reaction to human, humanized, chimeric or murine monoclonal antibodies.
21. The Investigator judges that the subject will be unable to fully participate in the study and complete it for any reason, including inability to comply with study procedures and treatment, addiction, or any other relevant medical or psychiatric conditions.
22. Body weight  $> 130$  kg.

- 23. Previous treatment with FG-3019.
- 24. Inadequate IV access.

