#### 11.2.2 Definition of a Serious Adverse Event (SAE)

A **serious adverse event** is any adverse event or suspected adverse reaction that results in any of the following outcomes:

- Death,
- A life-threatening AEs (i.e., if in the view of the investigator or sponsor, the subject was at immediate risk of death at the time of the event). Life-threatening does not refer to an event which hypothetically might have caused death if it were more severe,
- Inpatient hospitalization or prolongation of existing hospitalization,
- A persistent or significant incapacity or substantial disruption of the ability to conduct normal life functions,
- A congenital anomaly or birth defect, or
- Other medically important events

Based upon appropriate medical judgment, important medical events that may not result in death, be life-threatening, or require hospitalization may be considered serious when, they may jeopardize the subject or subject and may require medical or surgical intervention to prevent one of the outcomes listed in this definition. Examples of such medical events include allergic bronchospasm requiring intensive treatment in an emergency room or at home, blood dyscrasias or convulsions that do not result in inpatient hospitalization, or the development of drug dependency or drug abuse. These events must be reported to the sponsor similar to SAEs.

- A clinical diagnosis of IPF progression and surgical procedures such as lung transplantation are expected in this patient population. Data for IPF progression is being collected an efficacy endpoint (Sections 3.2.2, 10.3.4.3). However, as these events are medically significant and may be associated with hospitalization, so they should be reported as SAEs.
- Other elective surgeries (example knee replacement, haemorrhoidectomy, mole removal etc.) may occur during the study period. They should not be reported as SAEs, but the diagnosis that warranted these procedures should be reported (especially if this is a worsening of a pre-existing medical history condition). Any complications of such procedures should be reported as AE/SAE based on seriousness criteria listed above.

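### PFS leaves out lung transplantation, which the protocol expects, so a subject transplanted before any listed event is censored for a disease-related reason

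*Protocol*

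**What the plan says.** Protocol 10.3.4.3 sets the clock and the event list: "PFS is defined as the time from randomization to the first occurrence of the following events during the study". The events are:

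1. "Death from any cause"
2. "Absolute decline FVC percent of predicted value of" at least 10%, not explained by intercurrent illness and confirmed on repeat spirometry
3. "Clinical diagnosis of progression of IPF"

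The Synopsis and 3.2.2 give the same three events under the name progression of IPF. They start the clock at Day 1, a difference that does not affect this point.

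Censoring is covered by one sentence: "If no PFS event is observed during the study, then PFS is censored at the last PFT assessment". There is no rule for transplantation and none for competing events. The comparison is a Cox model in the Safety Population.

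Transplantation appears in three other places in the Protocol:

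- 11.2.2 (SAE definition): "A clinical diagnosis of IPF progression and surgical procedures such as lung transplantation are expected in this patient population". It asks for both to be reported as SAEs, but says only of progression that the data also serve an efficacy endpoint.
- 5.2, exclusion 13: "High likelihood of lung transplantation (in the opinion of the Investigator) within 6 months after Day 1".
- 1.1: it is described as the only treatment that improves survival, though age or comorbidity rules out most IPF patients.

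The supplied SAP is Part 2. It covers the extension descriptively and mentions neither PFS nor transplantation. Its introduction places the randomized-period analyses in Part 1, which was not supplied.

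**The concern.** A Cox model treats a censored subject as having the same future risk as those still under observation with the same covariates. A transplanted subject does not fit that assumption. Transplantation is a response to advanced lung disease, and on the Protocol's own account in 1.1 it improves survival, so it can delay or prevent the death that PFS would have counted. If none of the three listed events came first, the plan records the subject as event-free up to the last PFT.

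At stake is the validity of the between-arm PFS comparison. If transplants fall unevenly between arms, the arm with more of them looks better than it should. With about 136 subjects, a handful of cases can move the estimate.

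**Working it through.** **1. The plan's own figure.** The only power statement (Protocol 10.1) concerns the primary endpoint: 55 per arm, 10% dropout, SD 7.3, difference 4.2, two-sided 0.05, about 80% power. With 55 × 0.9 = 49.5 per arm, a two-sample t-test gives 80.9% and the normal approximation 81.7%, so it reproduces. It says nothing about PFS, for which no event count, hazard ratio or power is stated. Nothing below changes the primary sample size.

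**2. What the rule does to a transplanted subject.**

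| Course | Result under 10.3.4.3 |
|---|---|
| Confirmed FVC fall or recorded clinical progression, then transplant | Event, at the earlier date |
| Transplant, no earlier listed event, death later observed in the study | Event, at death |
| Transplant, no listed event before or after | Censored at last PFT |

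The third row is the problem. The last PFT may precede surgery. If the subject stays on study it may follow surgery, and time with a donor lung then counts as progression-free. Nothing in the supplied text prevents this.

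**3. Does the third component absorb transplants?** It has no criteria. An investigator could record clinical progression at or before surgery, but 11.2.2 names the two as separate items and links only progression to the efficacy endpoint. Whether a transplant counts is left to each of about 60 centers.

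**4. How many subjects?** The documents give no rate. At an assumed 1% to 5%, 136 × 0.01 = 1.4 and 136 × 0.05 = 6.8, so about 1 to 7 subjects. Only those with no earlier listed event matter, so the relevant number is at most this.

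**5. Effect on the estimate (all counts assumed).** Take equal arms with 15 listed events on FG-3019 and 25 on placebo. The crude event ratio is 15/25 = 0.60. Now count four transplants:

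| Split (FG-3019 / placebo) | Ratio |
|---|---|
| 0 / 4 | 15/29 = 0.52 |
| 2 / 2 | 17/27 = 0.63 |
| 4 / 0 | 19/25 = 0.76 |

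Leaving transplants out understates the drug effect in the first row and overstates it in the third. These are ratios of counts, not hazard ratios.

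**6. Effect on power (assumed).** Schoenfeld's approximation is power = Φ(|ln HR| × √d / 2 − 1.96), where d is the number of events. At HR 0.6:

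- d = 40: 0.511 × 6.325 / 2 − 1.96 = −0.345, power 36.5%
- d = 41 (one transplant added, 1/41 = 2.4% of events): 37.3%
- d = 46 (six added, 6/46 = 13.0% of events): 41.0%

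The gain in power is small. The case for the change rests on bias.

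**7. Are the data there?** Protocol 11.3.1 ends mandatory AE and SAE collection 4 weeks after the last dose. PFS counts events during the study, with no stated cut-off. A transplant after the SAE window need not be recorded.

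**The case against.** The strongest reply is that PFS is an unpowered secondary endpoint in a Phase 2 trial, most patients are not transplant candidates, and many who are transplanted will already have had a confirmed FVC fall or recorded progression. Treating transplantation as an event, a competing event or a censoring event can each be defended. All of this limits the size of the problem. It does not remove it, because the plan makes no reasoned choice among the three: the default rule censors, for an event that the Protocol itself anticipates.

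A reader might go further in four ways that the documents do not support:

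- *Every transplanted subject is censored as progression-free.* No. An earlier listed event or an observed death already counts.
- *The omission favours FG-3019.* The direction depends on how transplants split between arms, which is unknown.
- *A post-transplant FVC would distort the primary rank analysis.* Protocol 10.3.4 and 10.3.4.1 leave the imputation and ranking rules to the SAP, and SAP Part 1 was not supplied. Appendix 3 also puts end-of-treatment spirometry preferably 3 weeks after the last dose, and Section 8 makes efficacy assessments on withdrawal discretionary, so such a value would be unusual. A clarifying sentence is worth having, but no defect in the primary analysis is shown.
- *Exclusion 13 is wrong because six months (26.1 weeks) falls short of Week 48.* The remaining 21.9 weeks (46%) do lie outside it. But it is a baseline forecast of high likelihood in the investigator's opinion, not a bar on transplantation, and the shorter horizon is not an error.

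**Conclusion.** The point holds in a limited form. As written, the PFS definition censors a subject transplanted before any listed event, for a reason linked to the disease, although the Protocol expects transplants and names them apart from progression. That is informative censoring produced by a stated rule.

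Neither the direction nor the size of the bias can be derived from the documents. The 0.52 to 0.76 range rests on assumed counts (15 versus 25 listed events, four transplants) and shows only that a few cases could matter. The primary endpoint's sample size and power are unaffected. The conclusion covers the Protocol and SAP Part 2. SAP Part 1 may hold a transplant rule, but the Protocol's event list would still omit transplantation. The gap should be closed before unblinding.

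**What to change.** - In the Synopsis, 3.2.2 and 10.3.4.3, add lung transplantation as a PFS event, dated at surgery.
- Prespecify a sensitivity analysis that censors at transplant, so that the effect of the choice is visible.
- Record the transplant date through the end of PFS follow-up, not only within the SAE window of 11.3.1.
- State that FVC, HRCT and SGRQ values obtained after transplant are not used. If SAP Part 1 already says this, cross-reference it.

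No change to exclusion 13 is needed.

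The cost is small: a slightly broader composite, wording in three Protocol sections and the SAP, and one date field collected somewhat longer than SAEs are now. Most transplants during treatment would already be reported as SAEs under 11.2.2.
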